3.2. Summary of Clinical Findings

Three Phase 1 studies and two Phase 2a study have been conducted with buntanetap. For the three Phase 1 studies, the first was a single ascending dose (SAD) study in healthy volunteers; the second was a multiple ascending dose (MAD) study in healthy volunteers, and the third one was a pharmacokinetic (PK)/pharmacodynamic study of CSF obtained from mild cognitively impaired participants (Protocol QR12001). One Phase 1/2 study (Discover) was to test the safety, tolerability, PK and PD of buntanetap in subjects with early Alzheimer's disease (Protocol

QR12005). The other Phase 2a study was a double study for both early AD and early PD subjects to test buntanetap's safety, pharmacokinetics, biomarkers and efficacy (Protocol ANVS-12003).

In the SAD trial, buntanetap was administered orally in doses of 10, 20, 40, 80, and 160 mg. Limiting side effects observed following the 160 mg dose resulted in curtailment of the study without administration of the 320 mg dose. The 160 mg dose was associated with an increased incidence of nausea and vomiting (four subjects were nauseous and three vomited). Adverse events were either mild or moderate; none were severe. Buntanetap 80 mg was determined as the no observed adverse effect level.

Following oral administration, peak concentration was achieved rapidly, with mean observed T_{max} between 1.3 and 1.6 hours for both males and females at all doses. C_{max} increased disproportionately with increasing dose, as did the various measures of AUC. Differences in mean observed C_{max} and AUC between males and females at each dose appeared to be related to body weight rather than gender differences.

In the MAD trial, buntanetap was administered orally in doses of 20, 40, and 60 mg 4 times a day (QID). The first two treatments were dosed for 7 days, and the third, for 10 days. Single doses were given on the first and last day to determine the pharmacokinetics of the drug. In general, the drug was well tolerated, resulting in no serious or severe adverse events and only one premature discontinuation, a subject in the 60 mg group discharged because of nausea, vomiting, dizziness and "feeling warm." The incidence of adverse events, all either mild or moderate severity, also occurred with similar frequency in the placebo group. The most common AEs were dizziness, headache, and nausea/vomiting.

Buntanetap was absorbed rapidly after oral administration, achieving maximum plasma and CSF concentration (C_{max}) within 1.2-1.5 hours. For the 40 and 60 mg doses, with fully defined plasma profiles, the mean terminal $t_{1/2}$'s were 3.80 ± 0.88 and 5.23 ± 1.24 hours, respectively after a single dose and 3.53 ± 1.03 and 4.104 ± 0.91 hours, respectively, after repeat dosing. The half-life ($t_{1/2}$) of the plasma concentrations at the lower doses could not be calculated accurately. The C_{max} increased disproportionately with dose (24, 144, and 2310 ng.h/mL after a single dose of 20, 40, and 60 mg, respectively and 110, 134, and 2101 ng.h/mL after multiple doses of 20, 40, and 60 mg, respectively).

In the proof of mechanism of action study (Protocol QR12001), the PK of buntanetap was measured after 10 days of administration (4x60 mg) over 12 hours in CSF and plasma of the AD participants. The pharmacodynamics of a number of biomarkers was compared for 12 hours before the first dose at day 0 and after the last dose at day 11 of buntanetap administration. We found that the plasma concentrations of buntanetap overlapped with the plasma concentrations found in the MAD study. In this study, the N1-metabolite reached about 10 to 15%, while the level of the N8-metabolite reached about 20 to 25% of the buntanetap levels measured in plasma.

Because a substantial proportion of the adverse events observed in AD subjects treated with cholinesterase inhibitors appear to reflect the cholinomimetic properties of molecules in this

class, buntanetap's highest tolerated dose is determined by the levels of the N1-metabolite in blood and brain.

While the $t_{1/2}$ of buntanetap in plasma was 5 hours as seen in the SAD and MAD studies, the $t_{1/2}$ in CSF/brain was longer than 12 hours. The concentrations of buntanetap in the brain, extrapolated from blood and CSF, were 8 times higher than in plasma. 10 days of treatment with buntanetap normalized CSF levels of sAPP, tau, α SYN and a series of inflammatory markers. The concentration and persistence of buntanetap in the brain suggest that much lower doses of drug administered once daily could achieve the desired pharmacological effect.

For the Phase 2a trial (Protocol ANVS-12003), there are two parts of the study. In the first part, early AD and PD subjects were given 80 mg QD buntanetap or placebo for 25 days. In the second part, early PD subjects were given 5 mg, 10 mg, 20 mg, 40 mg QD buntanetap or placebo for 25 days. In all doses and in both AD and PD subjects, buntanetap was safe and well tolerated. No SAE was reported.

Buntanetap was absorbed rapidly after oral administration, achieving maximum plasma and CSF concentration (C_{max}) within 1-2 hours. For the 80 mg doses, with fully defined plasma profiles, the mean terminal $t_{1/2}$'s were 2.76 ± 2.668 hours. The half-life ($t_{1/2}$) of the plasma concentrations at the lower doses (5 & 10 mg) could not be calculated accurately. The C_{max} increased disproportionately with dose (15.31, 40.19 and 112.31 ng.h/mL after a single dose of 20, 40 and 80 mg, respectively).

Consistent with Phase 1 POC study, 80mg QD buntanetap reduced AD subjects' CSF levels of sAPPa, sAPPb, tau, phosphorylated tau (tau181), α SYN and a series of inflammatory markers (YKL-40, GFAP, sTREM2, Complement C3). Buntanetap also improved axonal integrity shown by Neurofilament light (NFL) and synaptic function shown by neurogranin (NG). Similarly, 80 mg QD buntanetap reduced PD subjects' CSF levels of α SYN and a series of inflammatory markers (YKL-40, GFAP, sTREM2, Complement C3). Buntanetap also improved PD subjects' axonal integrity shown by NFL and synaptic function shown by NG.

Further, buntanetap treatment improved AD subjects' cognition shown by ADAS-Cog11 and WAIS coding test and improved PD subjects' movement shown by MDS-UPDRS and WAIS coding test.

4.0 BACKGROUND AND STUDY RATIONALE

4.1. Background

A major pathological hallmark of PD is the appearance in the gut and in the brain of α SYN aggregates that form Lewy bodies. These aggregates are thought to occur one or two decades prior to overt symptom development. Recent research has shown that soluble forms of phosphorylated tau (p-tau) and other neurotoxic proteins such as TDP43 may also contribute to neuropathology of PD. A high load of inflammation and microglia activating factors that contribute to neurodegeneration are also common in PD.

Buntanetap is the (+) enantiomer of phenserine, an orally available small molecule. While phenserine inhibits AChE, buntanetap has no AChE activity itself and develops some activity in vivo with the metabolism to N1-bisnorposiphen. *In vivo*, phenserine has about 10-20 times more AChE inhibitory activity than buntanetap's metabolite N1-bisnorposiphen.

Buntanetap has been found to significantly reduce soluble APP and A β as well as tau, p-tau and α SYN in the rodent brain and in human CSF. In preliminary studies in animals and humans, inhibition of APP, A β , tau, p-tau and α SYN occurs at levels 8 to 16 times lower than the levels causing cholinomimetic effects.

Buntanetap acts at the 5'UTR of the α SYN and APP mRNA and lowers their protein expression levels in animal models; it also decreased α SYN and sAPP levels in human CSF. Our data suggests that these effects are achieved via the same mechanism: the 5'UTRs of these mRNAs form a complex with iron regulatory protein 1 and buntanetap stabilizes the complex, thereby inhibiting the translation of these mRNAs.

As buntanetap inhibits the synthesis of α SYN and APP, as well as other neurotoxic aggregating proteins, it might have a broader spectrum of activity than PD and AD. By protecting neurons from dying, it has a disease-modifying effect in PD, AD as well as other neurodegenerative disorders.

4.2. Study Overview

[figure not shown]
Study population: The study will be conducted in subjects with early PD.

Dose selection: Qualified subjects will be randomly assigned at a 1:1:1 ratio to one of the three treatment arms: buntanetap 10 mg, buntanetap 20 mg, and placebo.

Study Design: 450 early PD subjects will be randomized to 10 mg, 20 mg of buntanetap QD or placebo. They will undergo a Screening Visit, and if they provide informed consent and are considered eligible per the inclusion and exclusion criteria, will proceed to participate in the treatment period. Randomized participants will visit the clinic for the first-time dosing with administration of 10 mg or 20 mg of buntanetap or placebo, followed by an at home dosing period of 6 months, with daily administration of 10 mg or 20 mg of buntanetap or placebo. Participants will be required to attend clinic visits at 1 month, 2 months, 3 months, and 6 months (end-of-trial) time points, where they will undergo study procedures that include safety assessments (AE and concomitant medication monitoring, 12-lead ECGs, clinical laboratory testing, vital signs assessments, and physical/neurological examinations), psychometric tests (MDS-UPDRS, WAIS, MMSE) and PGIC and CGIS. After all end-of-study procedures are complete, the subject will be discharged to home. A 24-hour follow-up call will occur after all clinic visits to assess the participants current condition and if there are any additional adverse events to report.

Subjects who drop out during the initial 5 months at home treatment period will be discontinued and should complete an Early Discontinuation visit as soon as possible following discontinuation. Subjects that drop out after the initial 5 months, will be scheduled for an End of Trial visit. If 4 subjects are discontinued due to serious adverse events, a safety review will be conducted without interrupting the study. Unscheduled visits are allowed and investigators will perform safety assessments and AE/SAE and concomitant medication reviews as needed.

The following figure shows how many times and when these procedures will be performed throughout the approximately 7 months of the study duration:

4.3. Outcome Measures

Efficacy outcome measures: Buntanetap has shown to improve PD subjects' mobility. MDS-UPDRS sum of scores of Part II, Part III, Part II+III, and total score of first three parts will be measured to assess its improvement on PD subjects.

Safety outcome measures: Reports of adverse events (AEs) and serious adverse events (SAEs) during exposure to buntanetap will be collected to evaluate if there are any significant clinical safety issues for the study population. Extensive clinical and laboratory safety data already exist for buntanetap; therefore, these safety measures will be sufficient in the proposed study.

Clinical, functional and cognitive assessment measures: The subjects will be administered the [Hoehn & Yahr \(1967\)](#) and the [MMSE \(Folstein 1975\)](#) for determination of inclusion into the study. The MDS-UPDRS ([Goetz 2008](#)), Clinical Global Impression of Severity (CGIS, [Hurst 2004](#)), and Participant Global Impression of Change (PGIC, [Hurst 2004](#)) will be administered for subjects' movement and daily function. The Coding subtest from the Wechsler Adult Intelligence Scales, 4th edition (WAIS-IV; [Wechsler 2008](#)) will serve as a sensitive measure of CNS dysfunction. MMSE will also be measured to assess subjects' cognitive change.

Exploratory measures: Buntanetap has shown to reduce inflammation and preserve axonal integrity and synaptic functions as well as neurotoxic proteins in previous Phase 2a studies. In this study we plan to measure plasma GFAP, NFL and potentially TDP43 depending on assay availability.

5.0 POTENTIAL RISKS AND BENEFITS OF INVESTIGATIONAL PRODUCT AND STUDY PROCEDURES

5.1. Risks and Benefits Associated with Buntanetap or Placebo

There are no benefits to the subjects other than receiving medical and selective functional and cognitive evaluations.

The clinical investigator must advise all potential subjects of the possibility of unexpected side effects and carefully evaluate each person exposed to Investigational Product for possible AEs.

Side effects to placebo are not uncommon but are obviously not due to a pharmacological agent as an industry standard placebo (inactive ingredients) will be provided. The placebo used for the study consists of standard (non-lactose) pharmaceutical excipients which are generally recognized as safe (GRAS), with no known side effects anticipated.

Buntanetap has been tested in animal safety studies. No adverse effects were observed in rats given doses up to 40 mg/kg/day for 26 weeks. Drug-related effects observed in dogs included severe tremors at \geq 20 mg/kg/day, ataxia and gastrointestinal erosion/ulcer/inflammation at \geq 30

mg/kg/day, convulsions at ≥ 60 mg/kg/day, and duodenal necrosis and death at 100 mg/kg (equivalent to a human dose of 3,350 mg).

In clinical studies to date, buntanetap has been well tolerated with single doses of 80 mg or less and QID doses of 60 mg up to 25 days. A higher single dose of 160 mg was associated with an increased incidence of nausea and vomiting, potentially cholinergic based side effects, which resulted in the decision not to test higher single doses. Aside from nausea and vomiting, which are well-known responses to treatment with AChE inhibitors, the only consistent pattern of AEs entailed dizziness/fainting, headache, and reduction in total serum protein. These effects were seen to varying degrees at all doses of buntanetap and also in the placebo group. There was a tendency, but no definitive pattern of increased incidence of AEs with increasing dose of buntanetap. There have been no SAEs in prior clinical studies with buntanetap.

Definitive reproductive and developmental toxicity studies have not been conducted with buntanetap. As a result, women of childbearing potential will be excluded from participating in this study unless they agree to be on contraceptive for the whole duration of the trial and one month after. Female partners of male participants of childbearing potentials will also need to agree to be on contraceptive for the whole duration of the trial and one month after. Male study participants should not donate sperm and female study participants should not donate eggs during the whole duration of the trial and one month after.

At this time, there is no controlled clinical data available for anyone receiving SARS-CoV-2 (COVID-19) vaccination while being treated with buntanetap. However, based on the intended mechanism of actions and currently available data for these vaccine candidates and for buntanetap, it is not believed that there are specific risks to consider in subjects participating in this study who have received SARS-CoV-2 (COVID-19) vaccination or who are planning to receive the vaccination. As such, SARS-CoV-2 (COVID-19) vaccination is not prohibited. If appropriate, SARS-CoV-2 (COVID-19) vaccination should be considered as a concomitant medication (see Section 7.8.2).

5.2. Risk/Benefit Associated with Blood Collections

Phlebotomy is associated with mild to moderate discomfort due to piercing of the skin. This can be minimized with the use of a well-trained phlebotomist/nurse. Sometimes the blood draw site may become discolored with a “bruised” appearance that is transient and not painful. Rarely, the blood draw site may become infected and require antibiotic treatment.

6.0 SAMPLE SIZE AND STATISTICAL PLAN

A sample size of up to 450 subjects (1:1:1 randomized to 10mg, 20mg buntanetap and placebo respectively) is planned.

Definitions of the analysis populations and a detailed description of the analysis rules will be presented in a separate Statistical Analysis Plan (SAP).

6.1. Randomization

Subjects who have signed an informed consent and meet screening eligibility requirements will be randomly assigned to the active and placebo treatment groups at 1:1:1 ratio.

6.2. Power and Sample Size Determination

Qualified subjects will be randomized at a 1:1:1 to one of the following three treatment groups: 10 mg, 20 mg QD buntanetap and placebo. A sample size of 360 (120 per treatment group) will have 90% power to detect a treatment difference at a two-sided 0.025 significance level. In the sample size calculation, it was assumed a treatment difference of 2.55 and a common standard deviation of 5.59 based on historical data of MDS-UPDRS Part II+III (details will be provided in the Statistical Analysis Plan (SAP). Approximately 450 subjects will be randomized (approximately 150 per arm) to account for 112 patients calculated from the power analysis plus screen failures and dropout rates.

Based on FDA recommendations, the primary endpoint was changed into MDS-UPDRS Part II after enrollment ended. The current enrolled subject number gives us 90% power to detect a treatment difference of 3 points and a common standard deviation of 8 points of MDS-UPDRS Part II.

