#### 6 Determination of Sample Size

A sample size of up to 450 subjects (1:1:1 randomized to 10 mg, 20 mg buntanetap and placebo respectively) was determined.

Qualified subjects will be randomized at a 1:1:1 to one of the following three treatment groups: buntanetap 10 mg, 20 mg QD and placebo. A sample size of 360 (120 per treatment group) will have 90% power to detect a treatment difference at a two-sided 0.025 significance level. In the sample size calculation, it was assumed a treatment difference of 2.55 and a common standard deviation (SD) of 5.59 based on historical data of MDS-UPDRS Part II+III. Approximately 450 subjects will be randomized (approximately 150 per arm) to account for 120 subjects calculated from the power analysis plus screen failures and dropout rates.

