#### 8.10.2 Clarifications Based on Food and Drug Administration (FDA)'s Feedback

The interim analysis for sample size re-estimation has been completed in March 2023. Based on the interim analysis results and sample size re-estimation decision rules, the results of the interim analysis suggested to increase the sample size to 180 randomized subjects per arm. As of June 9, 2023, the study has completed enrollment with a total sample size of 522 (174 per arm) subjects.

The original evaluable sample size was 120 per arm, and a 20% drop out rate was assumed, which rendered to a sample size of 150 randomized subjects per arm (120/0.8=150). Based on the blinded data review, we noticed a low dropout rate of approximately 6%. With this dropout rate, 180 per arm randomized subjects will lead to 170 (180\*0.94) evaluable subjects per arm, which is around 42% increase from originally calculated sample size of 120 per arm (170/120=1.42). The sample size increased was considered reasonably small (42%) based on the Metha and Pocock (2011) paper that the overall Type I error rate will not be inflated.

The sample size re-estimation for our 3-arm study was handled by the worst-case scenario rules in Table 3 below. The sample size re-estimation method evaluates the conditional power in relationship to a pre-specified decision rule defined by ranges of attainable conditional power values. Only an increase in sample size was possible under this approach if observed conditional power was within the Promising Zone.

Outcome	Worst-case Scenario Approach
Both doses Unfavorable	Study proceeds with originally planned sample size
One dose Unfavorable	Study proceeds with sample size re-estimation increase
One dose Promising	suggested by one dose comparison in Promising Zone
One dose Unfavorable	Study proceeds with originally planned cample size
One dose Favorable	Study proceeds with originally planned sample size
	Study proceeds with larger of the sample size re-
Both doses Promising	estimation increases suggested by two dose comparisons
	in Promising Zone
One dose Promising	Study proceeds with sample size re-estimation increase
One dose Favorable	suggested by one dose comparison in Promising Zone
Both doses Favorable	Study proceeds with originally planned sample size

Table 3. Worst-case Scenario Approach to Sample Size Re-estimation for Multiple Dose Comparisons

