According to Chen, Yuan and Li (2018), the bias and error rate using the original maximum likelihood estimator (MLE) point estimator and confidence interval should be small and appropriate to use in the final analysis. In addition, the interim analysis was done using the original primary endpoint MDS-UPDRS Part II+III. Based on the Agency's feedback, the original primary endpoint is changed to MDS-Page 24 of 28 UPDRS Part II, and MDS-UPDRS Part II+III is kept as a secondary endpoint. Thus, the results of interim analysis are not relevant to the new primary endpoint. With a sample size of 174 per arm, the study will have 90% power to detect a treatment difference of 3 assuming a common SD of 8, based on a 2-sided t-test with alpha of 0.025.

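### The SD assumed for Part II alone (8) is larger than the SD assumed for the Part II+III sum that contains it (5.59), so the two 90% power statements are jointly implausible

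*Protocol*

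**What the plan says.** Protocol 6.2 gives two sets of planning inputs, one after the other.

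- **Part II+III, the primary endpoint when the trial was sized.** The inputs are a difference of 2.55 and a "common standard deviation of 5.59 based on historical data of MDS-UPDRS Part II+III". The claim is: "A sample size of 360 (120 per treatment group) will have 90% power to detect a treatment difference at a two-sided 0.025 significance level". SAP section 6 repeats the same inputs and the same claim.
- **Part II, the current primary endpoint.** The protocol says the endpoint changed after enrolment ended, and that the enrolled number gives 90% power for a "treatment difference of 3 points and a common standard deviation of 8 points of MDS-UPDRS Part II". SAP 8.10.2 reports that enrolment closed with a "total sample size of 522 (174 per arm) subjects" and claims "90% power to detect a treatment difference of 3 assuming a common SD of 8", "based on a 2-sided t-test with alpha of 0.025".

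Protocol 2.2 defines Part II as scored 0-52, Part III as 0-132, and the sum as 0-184. A higher score is worse on both parts.

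Part II+III remains a formally tested endpoint. SAP 8.3.1 puts it first in the fixed sequence of secondary endpoints, tested at alpha 0.025 within each dose.

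The only source given for 5.59 is unspecified historical data. Protocol 6.2 defers the details to the SAP, and SAP 6 does not supply them. No source is given for 8.

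**The concern.** A component has been given a larger SD than the sum it belongs to. A sum varies less than one of its parts only when the other part moves strongly against it. Parts II and III are both severity scores running in the same direction, and neither document suggests that patients who improve on one tend to worsen on the other.

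Both power statements stand in current text, and each concerns an endpoint that will be formally tested. If the larger SD is nearer the truth, the trial is much less sensitive on Part II+III than the stated 90% suggests. That endpoint is the gate to the rest of the secondary sequence: if it fails for a dose, Part III, Total score, PGIC and CGIS cannot be formally tested for that dose. If the smaller SD is nearer the truth, the trial can detect a noticeably smaller Part II effect than the plan states. A reader cannot tell which of these trials was planned.

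**Working it through.** **Inputs.** Part II+III: difference 2.55, SD 5.59, 120 per arm (protocol 6.2, SAP 6). Part II: difference 3, SD 8, 174 per arm (protocol 6.2, SAP 8.10.2). Two-sided alpha is 0.025 in both, with equal allocation.

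**Step 1: reproduce the stated figures.** By the normal approximation, n per arm = 2(z₀.₉₈₇₅ + z₀.₉₀)² × SD²/difference², with (2.241 + 1.282)² ≈ 12.41.

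- Part II+III: 2 × 12.41 × (5.59/2.55)² ≈ 119.3, so 120 per arm. Exact t-test power at 120 is 89.9%.
- Part II: 2 × 12.41 × (8/3)² ≈ 176.5, so 177 per arm. Exact t-test power at 174 is 89.3%.

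Both agree with 90% to rounding. If the roughly 6% dropout in SAP 8.10.2 is applied to 174, about 163 per arm remain and the Part II power is 87.1%.

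**Step 2: can the two SDs describe the same patients?** Let s be the SD of the Part III change and r its correlation with the Part II change. Then

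Var(II+III) = 8² + s² + 2 × 8 × r × s = 64 + s² + 16rs.

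For negative r this is smallest at s = -8r, where it equals 64(1 - r²). The target is 5.59² = 31.25. Setting 64(1 - r²) = 31.25 gives r² = 0.512, so r = -0.715, at s = 5.72. Every other s needs a more negative r:

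| SD of Part III change | Correlation required |
|---|---|
| 4 | -0.76 |
| 5.72 | -0.715 |
| 8 | -0.76 |
| 10 | -0.83 |
| 12 | -0.92 |
| above 13.59 | impossible |

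**Step 3: consequences if r is zero or positive** (exact t-test, two-sided 0.025).

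- *SD 8 holds for Part II.* Then SD(II+III) ≥ √(64 + s²) ≥ 8. At the floor of 8, power for 2.55 points on the sum is 58.5% at 120 per arm and 76.5% at 174 per arm. Reaching 90% needs at least 246 per arm. These powers are upper limits, because the floor gives Part III no variability at all. For illustration only, using values that are not in the documents: with s from 5.59 to 12 and r from 0 to 0.5, SD(II+III) runs from 9.8 to 17.4 and power at 120 per arm from 41% down to 13%.
- *SD 5.59 holds for the sum.* Then SD(II) ≤ 5.59, and power for 3 points on Part II at 174 per arm is at least 99.7%. The difference detectable with 90% power is 3.523 × SD × √(2/174). This is at most 2.11 points, against 3.02 points at SD 8.

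**The case against.** The strongest reply is that nothing has been miscalculated. Power is conditional on its inputs, and each 90% follows from its own. That stands. A reader might infer that one of the two power calculations is arithmetically wrong, or that the two statements are logically incompatible. The documents support neither, since the SD pair is attainable at a correlation of -0.72 or lower. The issue is joint plausibility.

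A reader might also set 3 against 2.55 and conclude that the plan expects the drug to worsen Part III by 0.45 points. That does not follow. The 2.55 is an assumed difference, while the 3 is a difference the enrolled number can detect, and at fixed n a detectable difference simply scales with the SD. The two differences do not by themselves conflict.

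The correlation bound requires both SDs to describe the same kind of quantity. The 5.59 could come from another population or follow-up time, or from a model-adjusted analysis. This is a fair limit on the conclusion, and it is also why the missing source matters.

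Finally, the Part II+III inputs may be called history. An interim review reassessed that endpoint, enrolment has closed, and the MMRM estimates its variance from the trial data, so neither SD enters a test. It is true that no test result depends on either SD. But SAP 6 still presents the first calculation as the determination of sample size, the documents do not report the interim SD, and Part II+III is still tested. Nor does the plan state 90% power for Part II+III at 174 per arm. The 76% ceiling there shows the gate's likely sensitivity; it does not contradict a stated figure.

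**Conclusion.** The point holds as a conflict between two SD assumptions. If both SDs refer to change from baseline in comparable patients, they are compatible only with a Part II/Part III correlation of -0.72 or lower, which nothing in the documents supports. Under any zero or positive correlation, at least one statement misdescribes the trial's sensitivity. Either the 90% for Part II+III at 120 per arm should be at most about 58%, or the 90% for Part II at 174 per arm should be above 99%. The documents do not show which SD is nearer the truth, and both could be off. If 5.59 is right, the Part II statement is merely cautious. If 8 is right, the first gate of the secondary hierarchy is weaker than a reader of SAP 6 would suppose. The effect falls on how the trial's sensitivity is stated and on how a null Part II+III result would be read; the validity of the tests is untouched.

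**What to change.** Before unblinding:

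1. Compute the pooled blinded SD of the Month 6 change from baseline for Part II and for Part II+III. Pooling across arms inflates the SD very little: a true 3-point effect in both active arms would raise the variance from 64 to 64 + 9 × (2/3) × (1/3) = 66, which is an SD of about 8.1.
2. Give the source, population and time point of 5.59 and of 8, and say whether each is a raw or a baseline-adjusted SD.
3. From the blinded SDs, restate the power or detectable difference for both endpoints at the enrolled or evaluable number, in protocol 6.2 and in SAP 6 and 8.10.2.
4. Keep the Part II+III calculation, labelled as the record of how the trial was first sized.

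The cost is two blinded summary statistics and revised wording, with no extra patients, no alpha spent and no unblinding. The downside is that a stated power may become less favourable.
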